2.1 Study design

We are proposing a **non-randomized pilot evaluation** of a universal TPT initiation strategy within the context of TUTT implementation for PLHIV initiating or re-initiating ART. Clinics will be assigned to the novel TUTT-PT arm or standard TUTT implementation arm with the primary analysis focused on the proportion initiated on TPT within 7 days of ART start. This study will also assess the rate of new TB diagnoses, TB treatment initiation for those testing positive for TB, the prevalence of TB drug resistance at the time of TB treatment initiation, time to TPT initiation, and provider experiences with TUTT implementation and TPT provision, among others.

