2.4 Clinic selection

Among the 18 public sector health facilities that participated in Fedisa in the [name] district, 5 will be selected to participate in the study from the list of clinics below. Clinics were chosen based on the average number of PLHIV who initiated or re-initiated ART on a monthly basis in 2021 and 2022. In order to ensure we can achieve the required sample size; we will select the larger clinics (on the basis of ART (re-)initiations) for study participation. Among the five selected clinics, two clinics will be assigned to standard TUTT implementation, and three clinics will be assigned to TUTT-PT implementation.

District	Clinic	ART initiations 2021	Mean monthly initiations 2021	ART initiations 2022	Mean monthly initiations 2022
Matlosana	Majara Sephapho	230	19.2	133	14.8
Matlosana	Orkney	207	17.25	130	14.4
Matlosana	Gateway NM Pretorius PHC	201	16.8	104	11.6
Matlosana	Kanana	194	16.2	114	10.4
Matlosana	Alabama	159	13.25	162	13.5
Matlosana	Tsholofelo	146	12.2	118	9.8
Matlosana	Empilisweni	144	12	102	11.2
Matlosana	Khuma	120	10	109	9.1

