2.8 Outcomes and analysis

The primary outcomes are the proportion of PLHIV who initiate TPT within 7 days of ART start and the median time to TB treatment initiation for those who test positive for TB. ART initiators include clients who are ART naïve and those re-initiating ART after a lapse in treatment. Secondary outcomes are included in the table below. TB test results and TPT initiation will be ascertained from study source documents and all available data sources in the clinics, including but not limited to paper files, electronic files (Tier.NET and DHIS2), clinic registers, pharmacy records, and lab test results. Analytic approaches are described in the table below.

Table 1. Outcomes & analysis approach

	Outcomes	Data source	Statistical Test
Primary	Proportion of PLHIV who initiate TPT within 7 days of ART (re-)initiation	Paper files, electronic files, clinic registers, pharmacy records, lab test results	Chi-square
Primary	Proportion of PLHIV who initiate TPT and have a subsequent positive TB test result	Paper files, electronic files, clinic registers, pharmacy records, lab test results	Chi-square
Primary	Healthcare provider experiences with universal TB testing and TPT provision	In-depth interviews	N/A
Primary	Median time to TB treatment initiation for those who test positive for TB	Paper files, electronic files, clinic registers, pharmacy records, lab test results	Kaplan-Meier
Secondary	Proportion of PLHIV evaluated for ART (re-)initiation tested for TB within 7 days of ART start, stratified by TB symptom status	Paper files, electronic files, clinic registers, pharmacy records, lab test results	Chi-square
Secondary	Prevalence of active TB disease among PLHIV evaluated for ART (re-)initiation, stratified by symptom status	Paper files, electronic files, clinic registers, pharmacy records, lab test results	Chi-square
Secondary	Median time from ART initiation to TPT initiation	Paper files, electronic files, clinic registers, pharmacy records, lab test results	Kaplan-Meier
Secondary	Proportion of PLHIV diagnosed with TB who remain on TPT for 7 days or longer	Paper files, electronic files, clinic registers, pharmacy records, lab test results	Chi-square
Secondary	Prevalence of TB drug resistance at TB treatment initiation, stratified by TPT use at the time of TB diagnosis	Paper files, electronic files, clinic registers, pharmacy records, lab test results	Descriptive proportions

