4.1 Data collection tools

Table 2. List of data collection tools and intended use

Name of tool	Purpose	Schedule	Study arm
Screening form (S001)	Confirm potential participant meets study eligibility criteria	Enrolment	Both
Patient enrolment questionnaire (PT001)	Baseline demographic and health data collected from study participants	Enrolment	Both
Laboratory test results (LT001)	All laboratory test results	Enrolment and 3 months after enrolment	Both
TB Follow-up Visit (PT002)	To document participant follow-up visit (sputum collection, switch from TPT to TB tx) following a positive TB test result	Following positive TB test result	Both
Health Monitoring Call (HM001)	To monitor participants for any symptoms or adverse events after starting TPT	1 month after starting TPT	Both
Medical record review (MR001)	ART history, TPT history, TB diagnoses, TB treatment initiation and regimen changes, and TPT initiation	3 months after enrolment	Both
Health care worker interview guide (IG001)	Interview guide for assessing clinic level implementation determinants	3-6 months after study initiation	Both

Participant completion form (PC001)	To document patient study completion, withdrawal, and death	As needed, and at ~3 months after enrolment	Both
-------------------------------------	---	---	------

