4.2.4 Data security

All paper study records (e.g. consent forms) will be kept in a secure location accessible only to authorized study staff, investigators, and monitors.

5 Study limitations

This study has the following limitations:

- As this is a non-randomised pilot, inferences of our results will be limited.
- Some new ART clients may be unwilling or unable to provide written informed consent to participate in the study. This may result in selection bias in our study population and limit generalizability.
- The presence of a PHRU study team research interviewer may influence routine TUTT implementation and TPT prescribing in standard of care clinics. We will minimize this influence by only enrolling participants into the study after the clinical consultation has been completed.
- Some participants may not own or have access to a mobile phone which is necessary for tracing of those who test positive for TB to initiate them rapidly on anti-TB treatment. To mitigate delays in anti-TB treatment initiation, all participants will consent to a household visit for tracing purposes if they do not have or do not answer their mobile phone.

6 Appropriate care in response to study-specific findings.

Participants in both TUTT-PT and routine TUTT implementation clinics who test positive for TB will be traced by a PHRU study team tracer and initiated on anti-TB treatment. The tracer will aim to return the participant to the clinic within 72 hours of sputum collection (48 hours for return of results and an additional 24 hours to trace the participant). The PHRU study nurse will refer participants to clinic staff for switch from TPT to anti-TB treatment in TUTT-PT participating facilities and clinic staff will initiate anti-TB treatment in routine TUTT implementation clinics. All participants who test positive for TB will be requested to provide additional sputum specimens (1) as per routine care and (2) for study-specific culture and drug susceptibility testing. Those with evidence of drug resistance will be referred to a doctor for further review and drug-resistant TB treatment initiation, as necessary.

7 Protection of human participants

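### The primary comparison of TPT initiation within 7 days is an unadjusted chi-square between non-randomised clinics, although individual covariates are collected in both arms

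*Combined protocol and SAP*

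**What the plan says.** Section 2.1 sets out a non-randomised design: "Clinics will be assigned to the novel TUTT-PT arm or standard TUTT implementation arm with the primary analysis focused on the proportion initiated on TPT". Section 2.4 gives the split: "two clinics will be assigned to standard TUTT implementation, and three clinics will be assigned to TUTT-PT implementation".

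Section 2.8 defines the analysis population as clients new to ART together with "those re-initiating ART after a lapse in treatment". It then says "Analytic approaches are described in the table below". In Table 1 the first primary outcome, "Proportion of PLHIV who initiate TPT within 7 days of ART (re-)initiation", has chi-square as its only method. No regression, stratification, standardisation or weighting is listed for it. Table 1 does stratify some secondary outcomes, by symptom status or by TPT use.

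Section 4.1, Table 2, lists two relevant forms for both arms. PT001 is completed at enrolment: "Baseline demographic and health data collected from study participants". MR001, a record review at 3 months, covers ART and TPT history. Section 5 concedes: "As this is a non-randomised pilot, inferences of our results will be limited". It names no analytic response.

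**The concern.** Nothing in the design balances the arms on participants' own characteristics. Each arm is a different small set of clinics, so the share of re-initiating clients, age, sex and symptom status may differ between arms. If any of these also affects whether TPT is started within 7 days, a crude chi-square counts the imbalance as part of the arm difference.

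Enrolment order adds another route. Under section 2.6, standard-arm clients reach the study nurse after TPT prescribing is complete. Under section 2.5, TUTT-PT clients are enrolled first and then referred for TPT. The kinds of client who consent could therefore differ.

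At stake is the comparison on which section 2.9 sizes the study. An imbalance could create part of the 15-point difference or hide part of it. Covariates to address the measured part are already due to be collected.

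**Working it through.** **Inputs from the documents.** TPT initiation of 65% versus 80%, 80% power, 5% significance, design effect about 1.3, and 200 per arm (section 2.9). Section 2.9 also gives a total of 450, which does not equal 200 + 200; I use 200 per arm. Sidedness is not stated; I assume two-sided.

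**Reproducing the plan's figure.** The usual two-proportion formula gives 138 per arm, or 151 with continuity correction. Then 151 × 1.3 = 196.3, so 197, close to 200. Without the correction, 138 × 1.3 = 179.4, so 180. Power with 200 per arm at design effect 1.3 (effective n = 200/1.3 = 153.8, no continuity correction) is 84%. The calculation treats all 15 points as the arm effect.

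**Bias formula.** Let r_T and r_C be the re-initiator shares in the TUTT-PT and standard arms, and p_R and p_N the TPT uptake in re-initiating and ART-naive clients. Suppose uptake within each client type is the same in both arms, so there is no true effect. The crude difference is then

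(r_T − r_C) × (p_R − p_N).

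**Assumptions.** The documents give none of these four quantities. I take a share difference of 10 to 30 points and an uptake difference of 10 to 40 points:

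- smallest: 0.10 × 0.10 = 1 point
- examples: 0.20 × 0.20 = 4 points; 0.20 × 0.30 = 6 points
- largest: 0.30 × 0.40 = 12 points

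Against the planned 15 points, that is 1/15 = 7% to 12/15 = 80%. The sign can go either way.

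**Rejection with no true effect.** Normal approximation centred on 65%, 200 per arm: SE = √(2 × 0.65 × 0.35 / 200) = 0.0477. The test rejects when the observed difference exceeds 1.96 × 0.0477 = 0.0935 in either direction. If the 1.3 design effect is present but the chi-square ignores it, the true SE is 0.0477 × √1.3 = 0.0544 with the same threshold.

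**Power if the bias runs the other way.** A true 15-point effect shows as 15 minus the bias. Base 65%, effective n = 153.8.

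| Bias (points) | Rejects, no clustering | Rejects, design effect 1.3 ignored | Power if the bias masks a true 15 points |
|---|---|---|---|
| 0 | 5% | 8.6% | 84% |
| 2 | 7% | 11% | 72% |
| 4 | 13% | 17% | 56% |
| 6 | 24% | 27% | 40% |
| 9 | 47% | 47% | 20% |

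Taking 65% as the lower of the two rates, rather than the centre, changes little: at 6 points, 25% without clustering and 28% with it. At 12 points the no-clustering figure is 71%.

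The second column isolates case mix. The third is closer to the plan's own assumptions, where the starting point is about 8.6%, not 5%, before any case-mix bias. The power column already includes the design effect, so it should not be paired with the second column as if they shared a basis.

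**Room for a model.** At the planned rates, 200 × 0.35 + 200 × 0.20 = 110 participants would not start TPT. Five coefficients (arm, ART status, age, sex, symptoms) leave 110/5 = 22 such participants each.

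**The case against.** The strongest objection is that the harm is assumed. The documents support neither a particular imbalance nor a particular uptake gap. All candidate clinics are listed under one sub-district, the five are chosen by the same volume rule (section 2.4), and eligibility is identical in both arms (section 2.3). A 30-point share difference together with a 40-point uptake gap has no support in the text, and at 1 or 2 points the effect is nearly harmless. This stands: the range is illustrative, and its low end matters as much as its high end.

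A reader might infer that combining ART-naive and re-initiating clients is itself a mistake. The documents do not support that. Both groups are the target population in sections 2.1, 2.3 and 2.8, and the strategy is meant for both.

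It can also be said that this is a declared pilot with limited inference, and that adjustment cannot rescue two versus three clinics. Both are true. But section 2.9 still powers a formal comparison and section 1.1.4 intends it to inform policy. A general caveat does not replace using covariates already collected.

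Finally, the choice of covariates is partly judgement. ART status follows from the study's own definition of its population. Symptom status has direct support, since section 1.1.3 cites guidance that delays TPT in clients who screen positive. Age and sex are conventional; nothing in the documents shows that they drive prescribing.

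**Conclusion.** The point holds as a gap in the analysis plan. Following Table 1 as written leaves measured individual confounding in the primary contrast, and a better method is available from data already planned.

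Its size and direction cannot be determined from the documents. Under the stated assumptions the crude difference shifts by 1 to 12 points either way. The false-positive rate runs from barely above nominal at 1 or 2 points to about 24% at 6 and 47% at 9, before the clustering that the chi-square also ignores.

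Two stronger readings should be resisted. The text does not show that most of the 15-point effect would be spurious; the 80% figure needs the extreme of both assumed ranges. Nor would adjustment turn the result into a secure causal effect of TUTT-PT, because differences between the clinics themselves would remain.

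**What to change.** For the first primary outcome in Table 1, keep the crude difference and pre-specify beside it an adjusted risk difference. Obtain it from a regression of TPT within 7 days on arm, ART-naive versus re-initiating, age, sex and baseline TB symptom status, standardised to the pooled sample. Report TPT initiation by arm separately for ART-naive and re-initiating clients.

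Make the interval for both differences allow for clustering by clinic in line with section 2.9. Inflating the variance by the 1.3 design effect is the simplest consistent choice, since a cluster-robust variance from five clinics is unreliable. State that symptom status is recorded in the same way in both arms: section 2.5 lists the symptoms, whereas section 2.6 mentions only a clinical evaluation.

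The cost is plan wording, a little more analysis and a modelling assumption; no new data source is needed. The adjustment removes measured individual case mix only, not clinic-level differences, and the report should say so.

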2.9 Sample size justification

We hypothesize that TPT prescribing will be 65% in routine TUTT implementation and 80% in TUTT-PT implementation. Thus, we will enrol 200 PLHIV in TUTT clinics and 200 PLHIV in clinics where they will receive TUTT-PT (450 total) in order to detect this difference with 80% power at a 5% level of significance while accounting for clustering by clinic (a design effect of approximately 1.3). A sample size of 450 will also enable us to identify an estimated 20 new ART clients diagnosed with TB (assuming prevalence of 5%) in order to evaluate time to TB treatment initiation. In addition, throughout study implementation, we will conduct ongoing monitoring of intervention safety, defined as the number of participants diagnosed with TB who remain on TPT after diagnosis by study arm.

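### The primary TPT comparison is planned as a bare chi-square although clinics are assigned and the sample size allows for clustering; at the plan's own design effect the 5% test runs at about 8.6%

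*Combined protocol and SAP*

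**What the plan says.** - **Unit of assignment.** Section 2.1: "Clinics will be assigned to the novel TUTT-PT arm or standard TUTT implementation arm". Section 2.4 gives the split: "two clinics will be assigned to standard TUTT implementation, and three clinics will be assigned to TUTT-PT implementation".
- **Sample size.** Section 2.9: "We hypothesize that TPT prescribing will be 65% in routine TUTT implementation and 80% in TUTT-PT implementation". The target is 200 participants in each arm, although the total is printed as 450. The size is chosen "in order to detect this difference with 80% power at a 5% level of significance while accounting for clustering by clinic", with the design effect put at about 1.3. No ICC is given.
- **Analysis.** Section 2.8 says "Analytic approaches are described in the table below". In Table 1 the row "Proportion of PLHIV who initiate TPT within 7 days of ART (re-)initiation" has one entry under statistical test: chi-square. No section mentions a design-adjusted chi-square, robust variance, GEE, mixed model or clinic-level comparison.
- **Limitations.** Section 5 says that inference is limited because the pilot is non-randomised. It mentions neither clustering nor the small number of clinics.

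**The concern.** A chi-square test on individuals treats them as independent. Here they come from five clinics, and sections 2.5 and 2.6 have clinic staff starting TPT in both arms, so the outcome depends partly on clinic practice. Section 2.9 accepts this when it sets the sample size. But inflating the sample protects power only if the analysis also uses the larger variance; it does nothing for the false-positive rate of an unadjusted test. If Table 1 is followed as written, ordinary variation between clinics could be reported as an effect of TUTT-PT, in a study that section 1.1.4 says is meant to inform policy.

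**Working it through.** **Inputs.** From section 2.9: 65% against 80%, 200 per arm, power 80%, significance level 5%, design effect (DE) 1.3. From section 2.4: 2 and 3 clinics. Assumed: a two-sided test (the plan does not say), equal clinic sizes within an arm, and any ICC above the one that 1.3 implies.

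**1. The plan's sample size.** The mean proportion is 0.725.
- Without continuity correction: n = [1.96 × √(2 × 0.725 × 0.275) + 0.842 × √(0.65 × 0.35 + 0.80 × 0.20)]² / 0.15² = 138 per arm.
- With continuity correction: 151 per arm. 151 × 1.3 = 197, which reproduces the stated 200.

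So the design effect really is built into the 200. The total of 450 is not reproduced and does not equal 200 + 200; that is a separate matter to reconcile.

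**2. True level of an unadjusted test at the plan's own DE.** The true variance of the difference is 1.3 times the one the test uses, so
2 × [1 − Φ(1.96 / √1.3)] = 2 × [1 − Φ(1.719)] = 0.086.

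**3. The ICC behind 1.3.** From DE = 1 + (m − 1) × ICC:
- 400 / 5 = 80 per clinic: ICC = 0.3 / 79 = 0.0038.
- 450 / 5 = 90 per clinic: ICC = 0.3 / 89 = 0.0034.
- Allowing for the 2 and 3 split at 200 per arm: about 0.0036.

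**4. If the ICC is larger.** At 200 per arm, clinics have 100 participants (standard) or about 67 (TUTT-PT).
- ICC 0.01: DE is 1.99 and 1.66, average 1.82; level 2 × [1 − Φ(1.96 / √1.82)] = about 15%.
- ICC 0.02: DE is 2.98 and 2.31, average 2.65; level about 23%.

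A beta-binomial simulation (200,000 replicates, 65% in both arms) agrees:

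| ICC | Plain chi-square | t-test on 5 clinic proportions, 3 df |
|---|---|---|
| 0.0036 (DE 1.3) | 8.7% | 4.6% |
| 0.01 (assumed) | 14.9% | 4.6% |
| 0.02 (assumed) | 23.2% | 4.8% |

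**5. What a valid analysis can deliver.**
- Naive standard error: √(0.65 × 0.35 / 200 + 0.80 × 0.20 / 200) = 0.0440. Half-width 1.96 × 0.0440 = 8.6 points.
- With DE 1.3: 0.0440 × √1.3 = 0.0502. The t quantile on 5 − 2 = 3 df is 3.182, so the half-width is 3.182 × 0.0502 = 16.0 points.
- Power for 65% against 80% on 3 df (noncentral t, with simulation as a check): 53% at DE 1.3, 41–43% at ICC 0.01, 31–33% at ICC 0.02. With 225 per arm (450 split evenly) and about the same clustering it is 56–58%.

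**The case against.** **Chi-square may be shorthand.** The entries in Table 1 are bare labels; Kaplan-Meier, an estimator, also appears in the test column. A reader might infer that the authors chose to ignore clustering, or that section 2.9 and Table 1 flatly contradict each other. The documents show less: an allowance made in the sample size and carried nowhere else. But section 2.8 points to Table 1 for the analysis, and followed as written the test is the unadjusted one. If an adjusted version was meant, it has to be stated.

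**Dividing the chi-square by 1.3 would be enough.** If 1.3 is right, this restores 5.0% and keeps about 84% power at 200 per arm. But it relies on a design effect for which the plan gives no basis. In the same simulation its level is 10.0% at an ICC of 0.01 and 17.3% at 0.02.

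**It is a non-randomised pilot.** This lowers the weight of any p-value, and confounding by clinic stays under every variance correction. Even so, section 2.9 commits to a 5% test.

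**Stronger readings the documents do not support:**
- *That every chi-square row is affected in the same way.* Two secondary rows (TB testing and TB prevalence) are stratified by symptom status, and their objectives name no comparison of arms.
- *That planned confidence intervals will be too narrow.* The plan specifies no interval for the arm difference.
- *That 15% or 23% is the expected error rate.* Those figures need ICCs that the documents do not give; only 8.6% follows from the plan's own design effect.

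**Conclusion.** The concern holds for the primary TPT-initiation row. The plan allows for clustering when it sets the sample size and then names a test that does not. On the plan's own design effect, a nominal two-sided 5% test has a true level of about 8.6%. That figure rests on 1.3 being right and on chi-square meaning the unadjusted test. The error grows quickly if the ICC is above about 0.004, but by how much cannot be settled from the documents. The 80% power claim does not survive a valid clinic-level analysis with five clinics: power is about 53% at the same inputs. The 16-point half-width exceeds the 15-point difference the study was sized to detect. This is the primary comparison, so the plan should be corrected before analysis.

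**What to change.** - **Table 1, primary TPT-initiation row.** Replace chi-square with a cluster-aware comparison: clinic proportions compared with a t distribution on 3 df, or an individual-level model with clinic as cluster and a small-sample correction named in advance. The clinic-level version was checked above and holds its level; the model was not, and with five clusters its correction needs care. Report the arm difference with its 95% CI and all five clinic proportions.
- **Section 2.9.** Restate the power: about 53% at 65% against 80%, 200 per arm and design effect 1.3, with a half-width of about 16 points (naive: about 9). Present the comparison as estimation or as exploratory.
- **Sparse TB outcomes.** With about 20 TB cases expected, 20 / 5 = 4 per clinic on average, a clinic-level t-test is not workable. Report these outcomes descriptively by clinic and arm.
- **Section 5.** Add clustering and the small number of clinics to the limitations, and say that the adjustment does not remove confounding from non-random assignment.

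**Cost.** Revised wording and a few lines of code; no new participants, visits or data. The real cost is giving up the 80% power claim and accepting a wider interval. Enrolling more people in the same five clinics would recover little, as the 225-per-arm figures show.
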